5.4. Required Medical Equipment

For the SpaceOAR System injection procedure, a real time bi-plane transrectal ultrasound (TRUS) and a stepper are required to provide clear, contortion-free images.

5.5. Relevant Medications

The administration of prophylactic antibiotics depends on clinical practice in investigation site and the patient's condition, which is at discretion of the doctors.

6. Study Objectives and Endpoints

6.1. Study Objectives

This study aims to evaluate the safety and performance of SpaceOAR System when it is used to create space between the rectum and prostate in men undergoing radiotherapy for localized T1-T2 prostate cancer in China via collecting the real word data of SpaceOAR System used, to generate local clinical evidence on Chinese patients.

6.2. Study endpoints

6.2.1 Primary endpoint

6.2.1.1 Primary effectiveness endpoint

The distance between the posterior prostatic capsule and anterior rectal wall post SpaceOAR hydrogel administration.

Measurement: The distance between the posterior prostatic capsule and anterior rectal wall is measured on the axial image slice closest to halfway between apex and base, from posterior edge of prostate to inner rectal wall via MRI.

6.2.1.2 Primary safety endpoint

AEs related to SpaceOAR system and/or procedure within 30 days following procedure will be observed.

6.2.2 Second endpoints

Functional Success

Defined as creation of at least 7.5mm space between the posterior prostatic capsule and anterior rectum wall as assessed via comparative pre and post SpaceOAR hydrogel injection MRI scans.

7. Study Design

This study is a retrospective and prospective, single arm, real world study. For those patients who have already received the SpaceOAR treatment before study kick-off, the data at baseline and the day of procedure will be retrospectively collected. For those patients who will receive SpaceOAR treatment after study kick-off, the clinical data at baseline, the day of procedure and 30 days post procedure will be prospectively collected.

All administration of SpaceOAR hydrogel will be performed by trained urologists in the hospital in Boao.

[figure not shown]

Figure 7-1 SpaceOAR System RWS Design

7.1. Scale and Duration

Up to 20 subjects with a pathologically confirmed diagnosis of clinical stage T1 or T2 prostate cancer indicated for radiotherapy will be enrolled in this study. This study is based on the use of licenced medical device in Hainan BOAO medical tourism pilot zone, the enrollment rate may be slow due to limited patients. The enrollment and 30 days follow up are expected to completed in 3 months.

7.2. Treatment Assignment

This is a single arm study without treatment assignment. All subjects will receive injection of SpaceOAR hydrogel at the hospital in Hainan BOAO medical tourism pilot zone.

7.3. Justification for the Study Design

SpaceOAR system has received CE Mark in 2010 and FDA approval in April 2015 respectively, and it is sold in many countries and regions with good safety and effectiveness. The pivotal study was a randomized control study, which provided a high level of evidence to verify its safety and effectiveness fully. This study aims to generate local clinical evidence on Chinese patients via collecting clinical data related to spacerOAR, which is based on the use of licensed medical device in Hainan BOAO medical tourism pilot zone. Due to limited patient in BOAO, the subjects will be enrolled prospectively and retrospectively, whose data will be collected.

7.4. Method to reduce biases

In order to reduce bias of the measurement of the distance between the posterior prostatic capsule and anterior rectal, MRI before and post procedure are suggested to be completed in same hospital.

8. Subject Selection

8.1. Study Population and Eligibility

The target population are Patients who have been pathologically confirmed prostate cancer with clinical stage T1-T2, and are appropriate for radiotherapy, and have been treated or will be treated with SpaceOAR Hydrogel in hospital in Hainan Boao Lecheng medical pilot zone.

8.2. Inclusion Criteria

Subjects who meet all of the following criteria may be given consideration for inclusion in this clinical investigation, provided no exclusion criterion is met.

- Subjects have provided the written informed consent, willing to participate in clinical data collection and willing to receive visit at 30 days post procedure. (for subjects enrolled prospectively)
- Subjects must have been pathologically confirmed prostate cancer with clinical stage T1-T2, and have been treated or will be treated with Space OAR Hydrogel in hospital in Hainan Boao Lecheng medical pilot zone.

8.3. Exclusion Criteria

This is a real world study, all patients who have received or are going to receive SpaceOAR procedure in Boao Medical Pilot Zone will be enrolled in this study. There is no specific exclusion criteria unless the patients refuse to sign the informed consent.

The indication and health status of subjects are assessed strictly by doctors before use of licenced medical device.

9. Subject Accountability

9.1. Point of Enrollment

For patients who have already received the SpaceOAR treatment, the clinical data can be collected retrospectively when he meets the inclusion criteria and the procedure recored is complete in reviewing medical recoreds. For patients who will receive the SpaceOAR treatment, informed consent will be performed.

9.2. Withdrawal

All subjects enrolled in the clinical study (including those withdrawn from the clinical study) shall be accounted for and documented. If a subject withdraws from the clinical investigation, the reason(s) shall be reported. If such withdrawal is due to problems related to device safety or performance, the investigator shall ask for the subject's permission to follow his/her status/condition outside of the clinical study. The applicable CRF, including the study end form, shall be completed by the time of subject withdrawal.(only for patients enrolled porspectively)

9.3. Lost to Follow-Up

A subject will be considered lost to follow-up if he fails to complete 30 days follow-up visits and is unable to be contacted by the study site staff after at least three documented attempts, at which point an End of Study form should be completed. Before a participant is deemed lost to follow up, the investigator or designee will make every effort to regain contact with the participant (where possible, 3 telephone calls and, if necessary, a certified letter to the participant's last known mailing address or local equivalent methods). These contact attempts should be documented in the participant's medical record or study file.(only for patients enrolled porspectively)

9.4. End-of-Study Definition

A subject is considered to have completed the study if he has completed all phases of study including the last visit or last scheduled procedure shown in the data collection schedule.

A clinical trial is considered completed when participants are no longer being examined or the last participant's last study visit has occurred.

9.5. End of Study Action Plan

A subject completes the study when he has received spaceOAR treatment and received 30 days follow up vist. In light of first use of the spaceOAR in Chinese patients, it is recommended that subjects could participate in the observational study after the injection of spcaceOAR, which is following part of this real word study.

10. Study Methods

10.1. Data Collection

The data collection schedule is shown in table 10-1 .

Table 10-1:Data Collection Schedule

Procedure/Assessment	Before procedure	Procedure	Post procedure	30 days post procedure (± 7 days)
Informed consent[#]	X			
Demographics	X			
Physical assessment, including weight and height	X			
Clinical diagnosis and clinical stage of tumor、 Gleason score	X			
Medical history (General disease, genitourinary history / treatment history)	X			
Questionnaires (IPSS, EPIC, QoL)	X			
Administration of SpaceOAR		X		
PSA	X			
CT&MRI[*]	X		X	
Concomitant medication		X	X	
Adverse event		X	X	X
Device Deficiency		X	X	X
PD[#]	X	X	X	X

Note:# only for patients enrolled prospectively;

*MRIs conducted in other hospital are allowed, ie, MRI completed in 30 days before procedure and in 10 days after procedure will be allowed in this study. MRI is required for patients with prostate cancer who receive radiotherapy; technical success and distance between the prostate and rectum will be evaluated based on MRI image.

10.2. Study Candidate Screening

After study kick-off, patients who have received treatment of SpaceOAR with a complete procedure recored in hospital in BOAO will be enrolled in this study, who compose retrospective cohort.

For patients who have been confirmed Prostate Cancer with clinical stage T1-T2 and will receive radiotherapy, is scheduled for SpaceOAR administration in hospital in BOAO will be enrolled in this study, who compose prospective cohort.

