11.2.2. Control of Systematic Error/Bias

All patients who receive the treatment of SpaceOAR in hospital in BOAO will be enrolled at a given time, no cherry-pick patients and data to reduce select bias.

11.2.3. The method of handling missing, incorrect data(including subjects withdrawal and lost to follow-up) and unreasonable data

Missing data will be excluded for primary analysis in this small sample size study. Incorrect and unreasonable data will be clarified before database lock. Imputation where applicable for continuous variable, and tipping point analysis where applicable for categorical variable might be conducted for sensitivity analysis.

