All deviations from the investigational plan, with the reason for the deviation and the date of occurrence, must be documented and reported to the sponsor using EDC. Sites may also be required to report deviations to the EC, and the regulatory authority, per local guidelines and national/government regulations.

Deviations will be reviewed and evaluated on an ongoing basis and, as necessary, appropriate corrective and preventive actions (including but not limited to EC/regulatory authority notification, site re-training, or site discontinuation/termination) will be put into place by the sponsor.

Considering that this study is a prospective and retrospective, real world study which is based on the 'pilot program' of licensed medical device, only collecting data, no intervention.

For data retrospectively collected, there is an chance of missing data, so missing data and undo test is not deemed to be deviations.

For prospective enrolled subjects who has signed ICF, Deviations must be recored, including but not limited to informed consent, inclusion criteria, follow-up visit etc.

15. Compliance

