4 GENERAL STATISTICAL METHODS

4.1 Analysis Sets

This study is a retrospective and prospective, real world study, in which subjects who received the treatment of SpaceOAR in hospital in BOAO will be enrolled.

The efficacy analysis set includes subjects with available distance measurement between prostate and rectum measured from MRI post procedure.

The safety analysis set includes all subjects who have received treatment of SpaceOAR in hospitals in Hainan BOAO.

All enrolled set: Retrospective subjects, who have already received the SpaceOAR treatment, are enrolled when they meet the inclusion criteria. Prospective subjects, who will receive the SpaceOAR treatment, informed consent will be performed for enrollment.

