4.2 Control of Systematic Error/Bias

All patients who receive the treatment of SpaceOAR in hospital in BOAO will be enrolled during the study period to minimize selection bias.

4.3 Method of handling missing, incorrect data (including subjects withdrawal and lost to follow-up) and unreasonable data

Missing data will be excluded for primary analysis in this small sample size study. Incorrect and unreasonable data will be clarified before database lock. Imputation with mean or median where applicable for continuous variable, and tipping point analysis where applicable for categorical variable might be conducted for sensitivity analysis. Visit-wise mean and LOCF imputation methods will be used for missing values.

Missing Event Dates Considerations:

For adverse events with missing event date (i.e., mm/dd/yyyy), the safety and/or data management representatives will query sites for missing data. In the event that the date for adverse event is missing at the time of analysis, please reference Section 7.4 for the missing/partial date handling rules.

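### Past patients have two conflicting entry rules, so the plan's stated safeguard against selection bias cannot be relied on or checked.

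*Protocol*

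**What the plan says.** **Narrow rule.** Protocol 10.2 (candidate screening) builds the retrospective cohort from those who have a full record: "patients who have received treatment of SpaceOAR with a complete procedure recored in hospital in BOAO will be enrolled in this study". Protocol 9.1 (point of enrollment) agrees: "the clinical data can be collected retrospectively when he meets the inclusion criteria and the procedure recored is complete in reviewing medical recoreds".

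**Wide rule.** Protocol 8.3, repeated in SAP 1.9, states that "all patients who have received or are going to receive SpaceOAR procedure in Boao Medical Pilot Zone will be enrolled in this study". The inclusion criteria (Protocol 8.2, SAP 1.8) do not mention the record. For the enrolled set, SAP 4.1 says: "Retrospective subjects, who have already received the SpaceOAR treatment, are enrolled when they meet the inclusion criteria".

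**Reliance on the wide rule.** Protocol 11.2.2 says of all treated patients that they "will be enrolled at a given time, no cherry-pick patients and data to reduce select bias". SAP 4.2 reads: "All patients who receive the treatment of SpaceOAR in hospital in BOAO will be enrolled during the study period to minimize selection bias". The only other bias measure, Protocol 7.4, concerns image measurement: "MRI before and post procedure are suggested to be completed in same hospital".

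**Missing past data.** Protocol 14 accepts gaps: "For data retrospectively collected, there is an chance of missing data, so missing data and undo test is not deemed to be deviations".

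**Safety.** The primary safety endpoint (Protocol 6.2.1.2) covers events related to the device, the procedure or both. The safety set (Protocol 11.2.1, SAP 4.1) is limited to subjects who received the treatment. Protocol 10.3 makes a consented man who does not receive it a screening failure. No section defines when treatment has been received.

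**The concern.** In a single-arm study with a retrospective part, the main protection against a favourable selection of past cases is to take every treated patient. The plan claims that protection and then sets an entry condition that can remove treated men. The condition is undefined and is applied at record review, after the procedure and its immediate outcomes have happened. The records under review also hold complications and device defects (Protocol 10.4.1).

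The subject accounting in Protocol 9.2 and SAP 5.2.4 starts from subjects already enrolled. A reader of the report therefore could not tell whether any treated man was left out, or why.

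The rate most exposed is the primary safety rate. It has a small denominator, and Protocol 20.2 provides for no clinical events or data monitoring committee. Protocol 17.4 says that the data are meant to support approval in China.

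**Working it through.** **1. The rules side by side, for a treated man who meets the inclusion criteria but has an incomplete procedure record**

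| Section | Entered? |
|---|---|
| Protocol 9.1 | No |
| Protocol 10.2 | No |
| Protocol 8.3, SAP 1.9 | Yes |
| Protocol 11.2.2, SAP 4.2 | Yes |
| SAP 4.1, all enrolled set | Yes |

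No section says which rule prevails.

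**2. The plan's own figure.** The documents give no figure for entry or for the safety rate. The one stated figure is the sample size (Protocol 11.1.1.2, SAP 3.1.2): mean 13 mm, goal 7.5 mm, so δ = 5.5 mm; σ = 5.7 mm; one-sided α = 0.025; power 90%.
- Printed formula: (1.960 + 1.282)² × 5.7² / 5.5² = 11.29, so 12.
- One-sample t-test, as named in SAP 3.1.3: power 89.1% at n = 13 and 91.5% at n = 14.

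The stated 14 is reproduced with the t-test. This point does not dispute it.

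**3. Effect on the safety rate.** Assumptions: 20 treated men; k are left out for an incomplete record; one of those k had the only related event. Intervals are 95% Clopper-Pearson, which the SAP names only for functional success. With no events, the upper limit is 1 − 0.025^(1/n).

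| Left out (k) | Reported | Upper limit |
|---|---|---|
| 0 (all entered) | 1/20 = 5.0% | 24.9% (lower limit 0.1%) |
| 1 | 0/19 | 17.6% |
| 3 | 0/17 | 19.5% |
| 6 | 0/14 | 23.2% |

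With 14 treated men and one left out, the contrast is 0/13 (0 to 24.7%) against 1/14 (7.1%; 0.2 to 33.9%).

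**4. Effect on the primary endpoint.** Assume that the entered men have mean 13 and SD 5.7, and that the k men left out have mean m and SD 5.7. For all 20, the lower limit is mean − 2.093 × SD/√20.
- k = 3, m = 0: mean = 17 × 13 / 20 = 11.05. Sum of squares = 18 × 5.7² + (17 × 3 / 20) × 13² = 1015.8. SD = √(1015.8/19) = 7.31. Lower limit 7.63 mm, still above 7.5 mm.
- k = 6, m = 7.5: lower limit 8.49 mm. With m = 5 it is 7.46 mm. It crosses 7.5 mm at m of about 5.1.

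Only the loss of many men with very poor spacing would change the conclusion.

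**5. The undefined term.** Take a consented man whose procedure is started and then abandoned before any gel is delivered. If receiving treatment means gel delivered, he is a screening failure and outside the safety set. If it means procedure begun, he is inside. Protocol 8.3 speaks of receiving the procedure and Protocol 11.2.1 of receiving treatment, so the text does not settle it. If he had the only related event, the contrast is again 0/19 against 1/20.

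The documents give neither an abandonment rate nor the split between cohorts, and the screening-failure sentence covers prospective men only. The chance of at least one such man is 1 − (1 − p)^n:

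| Assumed p | n = 5 | n = 10 | n = 20 |
|---|---|---|---|
| 1% | 4.9% | 9.6% | 18.2% |
| 5% | 22.6% | 40.1% | 64.2% |

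A related event in that same man is less likely still.

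**The case against.** **The size is hypothetical.** No document says how many past records are incomplete, and every safety contrast assumes that the omitted man had the only related event. The safety endpoint has no hypothesis or threshold, and step 4 shows the primary conclusion to be robust. All of this stands. It limits the severity but does not reconcile the sections.

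**The complete-record condition may be a sensible data-quality rule.** That is a fair motive. But Protocol 14 already tolerates missing retrospective items, and the increase from 14 to 20 subjects was made for missing data, so the plan does not need the condition. If the sponsor wants it, the claim of full enrolment must be qualified.

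**Stronger readings that a reader might infer, and that the documents do not support:**
- *The complete-record wording removes abandoned procedures.* It describes the record, and an abandoned procedure can be fully documented.
- *The plan excludes abandoned procedures from safety.* The screening-failure sentence can equally mean a man who never comes to the procedure. An event in an abandoned case would still be reportable (Protocol 18.1) and listed (SAP 5.2.5). This is an undefined term, not a shown exclusion.
- *The pivotal study's 99% placement success (Protocol 4.1) gives an abandonment rate.* Nothing says that the remaining cases were abandoned attempts.
- *Imputation could turn a man with no post-procedure scan into a functional success.* SAP 4.3 excludes missing data from the primary analysis and introduces imputation for sensitivity analysis. SAP 3.2 defines success by comparing scans before and after injection. SAP 7.3 also has a denominator sentence, though its reach is arguable.

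**Conclusion.** The conflict in retrospective entry is explicit and should be corrected. If Protocol 9.1 and 10.2 are followed, the control for selection bias claimed in Protocol 11.2.2 and SAP 4.2 does not hold, and nothing planned would reveal the men left out. Nothing in the documents shows that past patients have been or will be selected favourably; the point is that the report could not show otherwise.

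The size is at most moderate. One omitted man can decide whether a related event appears in a rate based on 14 to 20 men, for example 0% instead of 5.0%, on the assumption that he had the only such event. The safety endpoint is descriptive, and the primary effectiveness conclusion is not materially affected under the plan's own mean and SD.

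The undefined meaning of having received treatment is a secondary ambiguity. It should be closed because the endpoint itself counts procedure-related events.

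**What to change.** **Entry rule.** Delete the complete-record condition from Protocol 9.1 and 10.2, so that every treated man who meets the inclusion criteria is enrolled, up to the planned maximum of 20. Treat missing procedure items as missing data. In the disposition table (SAP 5.2.4), add the number of treated men identified and the number not entered, with reasons, including any left out because the maximum was reached. If the sponsor keeps the condition, define it and state it in Protocol 8.3 and 11.2.2 and SAP 1.9, 4.1 and 4.2. The log is needed either way.

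**Safety set.** Define the safety set to include started procedures, with the start tied to one recorded step chosen by the sponsor and the same rule in both cohorts. Limit screening failure to procedures never started. Read the treated wording of the inclusion criteria in the same sense. The planned 30-day phone contact would then also cover a prospective man whose procedure was abandoned.

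**Cost.** A protocol wording amendment with ethics committee approval (Protocol 13), an amended SAP (SAP 5.3), a count of treated men from site records, and very few extra phone contacts (10 × 0.01 = 0.1 expected with 10 prospective men at an assumed 1%). The safety rate may become slightly less favourable. The sample size and the primary effectiveness analysis do not change.

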10.3. Informed Consent

Retrospective cohort: For Patients who have received treatment of SpaceOAR before study kick-off, these relevant clinical data will be collected retrospectively. The study will be conducted according to study procedure approved by EC.

Prospective cohort: For patients who will receive treatment of SpaceOAR, the study will be conducted as usual prospective study, investigator will introduce study information to subject and and get ICF before procedure. Once the ICF is signed, he is considered to be participatie in study. If he fails to receive treatment of spaceOAR after ICF signed, the subjects is considered to be screening failure.

10.4. study visits

10.4.1. Retrospective cohort

For subjects who have received treatment of SpaceOAR, the relevant clincial data below will be collected and be entered in EDC.

- Before procedure: data at baseline will be collect, eg. demographics, physical assessment (height, weight), clinical diagnosis and clinical stage, Gleason score, PSA, CT, MRI and other related examinations, medical history, urinary history and surgery history etc.(Clinical diagnosis and clinical stage, Gleason score, CT and MRI from other hospital wthin 30 days before procedure are allowed, as applicable.)
- Procedure : collecting procedure information such as anesthesia, SpaceOAR dosage, intraoperative device usage, device defects (if any), complications, etc.
- Post procedure: CT and MRI of subjects will be collected retrospectively; Adverse events and device deficiency within 30 days post procedure(if any) will be retrospectively collected.(CT and MRI performed in 10 days after surgery are allowed.)

